15.7 Assessment of Dose Proportionality for SOBI003

Exploratory dose proportionality will be analyzed with the method originally described by Gough et al. (1995) (14) and modified as described by Smith et al. (2000) (15) and further adapted by Hummel et al. (2009) (16).

$C_{end\ of\ inf}$, AUC_{0-168h} will be analysed, and depending on the results other parameters may be analysed such as C_{max} , C_{min} and AUC_{0-inf} may also be analyzed. The general model $\log(C_{max}, C_{min}, C_{end\ of\ inf}, AUC_{0-168h}, AUC_{0-inf})$ for all doses and cycles where available) = $\mu + \beta \log(\text{dose})$ will be used to investigate the null hypothesis ($H_0: \beta=1$). Dose-proportionality will be rejected if the 90% CI of the estimated slope falls outside the critical interval. Patient's weight or age may be included as covariate.

The critical interval will be calculated as follows:

First the ratio (r) of the highest dose level to the lowest dose level will be calculated.

The lower limit of the critical interval will be calculated as: $\text{Log}(0.5)/\text{log}(r) + 1$.

The upper limit of the critical interval will be calculated as: $\text{Log}(2.0)/\text{log}(r) + 1$.

r value is based on the ratio between highest and lower dose levels of SOBI003 and equals to $20 / 3 \text{ mg/kg} = 6.667$

Thus, critical interval to declare dose linearity will be 0.63 to 1.37 for 90% CI of the slope estimate.

Additionally, PK parameters C_{\max} , C_{\min} , $C_{\text{End of inf}}$, AUC_{0-168h} , $AUC_{0-\infty}$ with total dose and body weight adjusted dose will be investigated using Pearson correlation analysis to estimate which type of dosing has an effect on pharmacokinetics of SOBI003.

The FISHER option in the PROC CORR statement will be used to estimate confidence limits and p-values for Pearson correlation coefficients based on Fisher's z transformation. Alpha value and a null hypothesis value will be specified for 95% two-sided CI.

The formula for sample Pearson product-moment correlation is:

$$r_{xy} = \frac{\sum_i (x_i - \bar{x})(y_i - \bar{y})}{\sqrt{\sum_i (x_i - \bar{x})^2 \sum_i (y_i - \bar{y})^2}}$$

Fisher z transformation is calculated as $z = 0.5 \log_e \left(\frac{1+r}{1-r} \right)$

CI's in addition to p-value will be calculated to demonstrate the validity of correlation.

Dose proportionality will also be explored graphically with plots of C_{\max} , AUC_{last} and AUC_{∞} vs body weight adjusted dose (mg/kg) or total dose (mg).

Dose proportionality plots will be presented for SOBI003 C_{\max} , C_{\min} , $C_{\text{end of inf}}$, AUC_{0-168h} , $AUC_{0-\infty}$. Regression/scatter plot in log-log and linear scales of PK parameters vs dose levels including body weight normalized and total dose will be presented.

16 Pharmacodynamic analyses

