14.3.4.8 Immunogenicity

Table 14.3.4.8.1	Number (%) of Patients with Anti-Drug Antibody (ADA) and Neutralizing Antibody (NAb) in Serum by Visit – Immunogenicity Analysis Set
Table 14.3.4.8.2	Number (%) of Patients with Anti-Drug Antibody (ADA) and Neutralizing Antibody (NAb) in Cerebrospinal Fluid (CSF) by Visit – Immunogenicity Analysis Set
Figure 14.3.4.8.3	Immunogenicity: Patient plots over Time – Immunogenicity Analysis Set

14.3.4.9 PK

Table 14.3.4.9.1	Summary of PK concentrations by Dose, Visit and Time point – PK Analysis Set
Table 14.3.4.9.2	SOBI003 PK parameters by Dose, Visit – PK Analysis Set
Table 14.3.4.9.3	Attainment of Steady State for SOBI003 using Repeated Measures ANOVA – PK Analysis Set

Table 14.3.4.9.4	Dose Proportionality for SOBI003 PK parameters by Visit using Humel Power Analysis – PK Analysis Set
Table 14.3.4.9.5	Dose Proportionality for SOBI003 PK parameters by Visit using Pearson Correlation Analysis – PK Analysis Set
Figure 14.3.4.9.6	Individual Serum PK Concentration-Time Profiles at Week 1, 4, 12, and 24 by Dose Level in Linear and Log-Linear Scales – PK Analysis Set
Figure 14.3.4.9.7	Mean (SD) Serum PK Concentration-Time Profiles at Week 1, 4, 12, and 24 by Dose Level in Linear and Log-Linear Scales – PK Analysis Set
Figure 14.3.4.9.8	Individual Trough and End of Infusion Serum PK Concentrations by Dose Level in Linear and Log-Linear Scale – PK Analysis Set
Figure 14.3.4.9.9	Mean (SD) Trough and End of Infusion Serum PK Concentrations by Dose Level in Linear and Log-Linear Scale – PK Analysis Set
Figure 14.3.4.9.10	Scatter Plots of Cerebrospinal Fluid PK Concentrations at Week 12 and 24 by Dose Level – PK Analysis Set
Figure 14.3.4.9.11	Regression/Scatter Dose Proportionality for SOBI003 in Log-Log and Linear-Linear Scales – PK Analysis Set
Figure 14.3.4.9.12	Regression/Scatter Dose Proportionality for SOBI003 in Linear-Linear Scales – PK Analysis Set

14.3.4.10 PD

Table 14.3.4.10.1	Heparan Sulphate (HS): Summary by Visit and Change from Baseline – Safety Analysis Set
Table 14.3.4.10.2	Summary of Heparan Sulphate (HS) Concentrations by Visit and Time point - Safety Analysis Set
Figure 14.3.4.10.3	Individual Serum Heparan Sulphate (HS) Concentration-Time Profiles by Dose Level in Linear and Log-Linear Scales – Safety Analysis Set
Figure 14.3.4.10.4	Individual Urine Heparan Sulphate (HS) Concentration-Time Profiles by Dose Level in Linear and Log-Linear Scales – Safety Analysis Set

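### The dose-proportionality rule in SAP 15.7 names no result for a confidence interval that crosses a limit, and its printed equation covers all cycles with no patient term although the planned table is by visit

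*SAP*

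**What the plan says.** SAP 15.7 fits the log of each PK parameter as mu + beta log(dose) and sets up a null hypothesis of beta = 1. The decision is worded twice. Rejection reads: "Dose-proportionality will be rejected if the 90% CI of the estimated slope falls outside the critical interval". Acceptance comes through the "critical interval to declare dose linearity will be 0.63 to 1.37 for 90% CI of the slope estimate".

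The limits are 1 + log(0.5)/log(r) and 1 + log(2.0)/log(r), with r = 20/3. The equation is to be fitted "for all doses and cycles where available". The only optional addition is a covariate: "Patient's weight or age may be included as covariate". No patient or visit term is printed.

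The output index in SAP 19.2 lists Table 14.3.4.9.4 as "Dose Proportionality for SOBI003 PK parameters by Visit using Humel Power Analysis".

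The section calls the analysis exploratory. SAP 4.1 says that 3 patients were included in each of Cohorts 1 and 2 and that Cohort 3 will not be started.

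**The concern.** There are two separate faults.

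**Decision rule.** An interval can lie wholly inside the limits, wholly outside them, or across one of them. The text covers the first two cases and leaves the third open. If outside is taken to mean not wholly inside, every crossing interval rejects proportionality, even when the true slope is exactly 1 and the only problem is six children. If it is taken to mean wholly outside, a crossing interval is not rejected, and the text does not say what is then concluded. Two analysts could report different conclusions from the same data.

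**Model.** Each child contributes several cycles. A regression over all of them with no patient term treats repeated values from one child as independent, so the interval for the slope is too narrow. Fits by visit, as the table title implies, do not have this problem. The text and the table need to agree.

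**Working it through.** **The plan's own interval.** With r = 20/3, ln 2 / ln(6.667) = 0.6931/1.8971 = 0.365, so the limits are 0.635 and 1.365. The printed 0.63 to 1.37 reproduces.

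**Limits for two cohorts.** Cohort 1 is 3 mg/kg. SAP 14.1 gives 10 mg/kg as planned for Cohort 2, but protocol Table 2 leaves that dose to the Safety Review Committee, so 10 mg/kg is an assumption here. Then r = 10/3, ln r = 1.204, 0.6931/1.204 = 0.576, and the limits are 0.424 and 1.576. Over a 3 to 10 mg/kg range the printed limits allow a departure of only (10/3)^(±0.365) = 0.64 to 1.55-fold, against the 0.5 to 2-fold that the formula is built on.

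**One value per child, 3 versus 3.** The 90% half-width is t(0.95, 4 df) × s × sqrt(2/3) / ln(10/3) = 2.132 × 0.8165 / 1.204 × s = 1.446 s, where s is the SD on the log scale. It exceeds 0.365 once s is above 0.253 (CV about 26%), and exceeds 0.576 once s is above 0.398 (CV about 41%). Beyond those points an interval of typical width cannot fit inside the limits.

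The documents give no PK variability, so the between-child CV is assumed. Simulated log-normal data with a true slope of 1 give these shares of trials in which the 90% interval crosses a limit:

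| Between-child CV | Printed limits, 0.63 to 1.37 | Limits for r = 10/3, 0.42 to 1.58 |
|---|---|---|
| 15% | 19% | 0.4% |
| 20% | 50% | 7% |
| 30% | 84% | 43% |
| 40% | 94% | 72% |

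Results differ by about a percentage point with rounding of the limits and the scale used for the CV. Crossing passes one half at a CV of about 20% with the printed limits and about 33% with limits for r = 10/3. At a true slope of 1 the interval is wholly outside in under 1% of trials for CVs up to 50%. Under the partly-outside reading, nearly all rejections would therefore come from imprecision.

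**Cycles pooled as printed.** SAP 15.3 derives parameters at Weeks 1, 4, 12 and 24, and at Weeks 16 and 20 as applicable, so 4 to 6 cycles per child. With k cycles and within-child correlation rho, the variance of a cohort mean is understated by a factor of about 1 + (k − 1) rho. For k = 4 and rho = 0.5 this is 1 + 3 × 0.5 = 2.5, so the standard error is too small by sqrt(2.5) = 1.58. The fit also claims 6 × 4 − 2 = 22 degrees of freedom, where the children supply 4. Simulated coverage of the nominal 90% interval:

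| Between SD, within SD | Correlation | 4 cycles | 6 cycles |
|---|---|---|---|
| 0.2, 0.3 | 0.04/0.13 = 0.31 | 75% | 68% |
| 0.3, 0.3 | 0.09/0.18 = 0.50 | 67% | 58% |
| 0.3, 0.15 | 0.09/0.1125 = 0.80 | 56% | 47% |

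Analysing one mean per child restores coverage to about 90%.

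**The case against.** **Crossing depends on assumptions.** A reader might infer that the analysis will usually give a verdict that the data cannot support. The documents do not establish that. The frequency rests on a CV they do not report and on a Cohort 2 dose they only call planned. Much of it also comes from using r = 20/3. With r = 10/3 and a CV of 20%, only 7% of intervals cross. This stands.

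**Pooling is not settled.** The phrase about doses and cycles could mean each cycle in turn, and the table title supports that. By-visit fits need no patient effect. This also stands: the model fault applies only if the equation is programmed as printed.

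**The two faults do not add up.** By-visit fits give wide intervals that cross often. Pooling gives falsely narrow ones that cross less: 37% against 87% with patient means (4 cycles, between-child CV 30%, within-child CV 20%, true slope 1, printed limits). They are alternatives.

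**Non-linear PK declared linear.** A reader might infer that clearly non-proportional exposure would be declared linear. That needs a rule that the SAP does not print, namely that anything not wholly outside counts as linear. The natural reading of declaring linearity is that the interval lies inside the limits. At a true slope of 0.4 and a CV of 30%, that happens in under 1% of trials with the printed limits and about 4% with limits for r = 10/3.

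**The cited methods and the status.** The SAP adopts a published approach, and those papers, which are not available here, may say how to treat a crossing interval. No p-value for the slope is planned, so the beta = 1 hypothesis may be only a framing of the interval rule. The analysis is exploratory, no decision is tied to it, and individual listings and plots will show the six children. These points lower the priority. They do not supply the missing outcome or settle which rows enter the model.

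**Conclusion.** Both faults hold, separately, in an exploratory analysis.

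The pooled model is wrong as written. If 4 to 6 cycles enter the printed equation without a patient term, coverage falls from a nominal 90% to about 47% to 75%, for assumed within-child correlations of 0.3 to 0.8. If the fits are by visit, the fault disappears, so the text and the table title must be reconciled.

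The decision rule is a cheap improvement. A crossing interval has no named result, and how often one occurs depends on the assumed CV, the assumed 10 mg/kg and the limits used. Over CVs of 20% to 40% the range is 50% to 94% with the printed limits and 7% to 72% with limits for r = 10/3. Harm follows if outside is read as not wholly inside, because imprecision alone then rejects proportionality.

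The value of r adds to this. SAP 15.7 uses the 20 mg/kg level, while SAP 4.1 says that cohort will not be started.

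**What to change.** In SAP 15.7:

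- State three outcomes. 90% interval wholly inside the limits: consistent with proportionality. Wholly outside: not proportional. Crossing a limit: inconclusive. Report the slope and interval in every case.
- Say that the interval criterion decides, not a test of beta = 1.
- Fit by visit, as Table 14.3.4.9.4 says. If cycles are pooled instead, add a random patient effect with Kenward-Roger degrees of freedom, as the second model in SAP 15.6 already does for trough concentrations, and change the table title.
- Compute r, and from it the limits, from the dose levels actually given. If these were 3 and 10 mg/kg, the same formula gives 0.42 to 1.58.

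The cost is a few sentences and at most one model line, with no new data. The downside is that the result may well be inconclusive, which is a fair description of what six children can show.

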Assessments for pharmacokinetic (PK) and pharmacodynamics (PD) evaluation:	
Serum concentration vs time profiles are obtained for determination of SOBI003 PK variables at Weeks 1, 4, 12 and 24. In addition, serum samples are collected when ADA samples are obtained. SOBI003 concentration in CSF is assessed at Weeks 12 and 24.
 
HS is assessed in CSF at Baseline and Weeks 12 and 24. HS in serum is assessed at Baseline and at Weeks 2 to 4, 8, 12 and 24. HS in urine are assessed at Screening, Baseline, and at Weeks 2 to 4, 8, 12, and 24.

Assessments for efficacy evaluation:	
Neurocognition is assessed by the BSID-III and/or KABC-II at Baseline and at Week 24. Adaptive behavior is assessed by the VABS-II at Baseline and at Week 24. Gray matter volume is assessed by MRIs at Baseline and at Week 24. The PedsQL is completed by the parent/primary caregiver at Baseline and at Weeks 12 and 24.

Assessments for exploratory PD evaluation:	
Clinical manifestations, including language, motor function, and sleep pattern are assessed at Baseline and at Week 24. Sleep pattern is also assessed at Week 12. Brain and abdominal MRIs are performed at Baseline and at Week 24 to assess ventricles, white matter, basal ganglia, and liver and spleen volumes.

Test product; dose and mode of administration:	
SOBI003, 20 mg/mL, concentrate for solution for i.v. infusion
 
3 dose levels are planned. The dose level for Cohort 1 is 3 mg/kg. The planned mid and maximum dose levels for Cohorts 2 and 3 are 10 mg/kg and 20 mg/kg, respectively. The dose levels for Cohorts 2 and 3 will be determined by the Safety Review Committee and will be based on review of pre-specified safety, tolerability, immunogenicity, PK and PD data

Reference product; dose and mode of administration:	Not applicable
Duration of treatment(s):	24 weeks

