7.4 Treatments

7.4.1 Treatments administered

In this open-label non-controlled study, the investigational medicinal product (IMP) is SOBI003. SOBI003 is administered as 4-hour i.v. infusions given once weekly for a duration of 24 weeks. In case of occurrence of infusion reactions, the infusion duration may be prolonged up to 24 hours at the discretion of the investigator.

Three dose levels of SOBI003 will be assessed, provided that the SRC concludes that the safety profile is acceptable. The planned lowest dose level is 3 mg/kg (cohort 1). For cohorts 2 and 3, the dose levels will be selected on basis of at least 4-week safety, PK, immunogenicity, and PD data of prior dose cohort(s) as well as applicable toxicology data (refer to Section 7.4.5). An additional cohort comprising 3 patients may be added, if deemed necessary for safety, tolerability, PK or PD evaluation.

SOBI003 solution, 20 mg/mL, is mixed with NaCl 0.9% infusion solution prior to administration. For a bodyweight < 25 kg, the total infusion volume is 100 mL. For a bodyweight \geq 25 kg, the total infusion volume is 250 mL.

Actual materials to be used for mixing SOBI003 solution with NaCl infusion solution (i.e., infusion solutions, syringes and needles) and for administering the infusions (i.e., infusion lines, syringes, manifolds, venous access ports) must be preapproved by Sobi to secure that all materials are compatible with SOBI003.

Detailed IMP preparation instructions are provided in a separate IMP manual.

Table 2 **Investigational medicinal products**

Cohort	Investigational product	Dosage form	Route	Weekly dose	Dosage regimen
1	SOBI003	Solution for infusion	i.v.	3 mg/kg	4-hour infusion given once weekly
2	SOBI003	Solution for infusion	i.v.	X mg/kg ¹	4-hour infusion given once weekly
3	SOBI003	Solution for infusion	i.v.	Y mg/kg ¹	4-hour infusion given once weekly

¹ Actual dose levels are determined by SRC (refer to Section 7.4.5).

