4.1 Overall study design and plan

This is an open-label, non-controlled, parallel, sequential ascending multiple-dose, multicenter study to assess the dose related safety, tolerability, pharmacokinetics (PK), and pharmacodynamics (PD) of SOBI003 in pediatric MPS IIIA patients. An overview for the study design is presented in [Figure 1](#).

In February 2020, Sobi decided to discontinue the SOBI003 program. At the time of the decision, 3 patients had been included in Cohort 1 and 3 patients in Cohort 2 of the FIH study (SOBI003-001). All patients had been enrolled in the Extension study (SOBI00-002) and will have the possibility to continue their treatment for a total of two years. Thus, Cohort 3 in the FIH study (SOBI003-001) will not be started. Statistical analysis for the FIH study (SOBI003-001) CSR will be done for Cohort 1 and 2.

Figure 1 Overview for study design for Study SOBI003-001

SOBI003 is administered as weekly intravenous (i.v.) infusions over a period of time of 4 hours. The study treatment period comprises 24 weekly infusions. Prior to initiation of each infusion, the patients are pre-treated with a single dose of non-sedative antihistamine. If infusion-related reactions occur, then the infusion duration may be expanded up to 24 hours and supportive medication may be administered, at the discretion of the investigator.

The study is planned to consist of 3 dose cohorts, each comprising 3 patients, provided that no significant safety concern arise. An additional cohort comprising 3 patients may be added, if deemed necessary to more accurately characterize the safety, tolerability, PK or PD.

The screening visit can be performed up to 12 weeks prior to the first SOBI003 infusion. At the screening visit, the MPS IIIA diagnosis is verified and the genotype is determined at a central laboratory. Patients are assigned to a dose cohort in consecutive order as the eligibility criteria have been confirmed, with prioritization of the younger patients.

Treatment initiations will be staggered within each cohort in order to be able to observe, interpret and treat possible adverse reactions and to ensure that such reactions can be dealt with promptly. For each cohort, safety review committee (SRC) meetings are scheduled approximately 3 weeks after completion of the 3rd patient's 4th dose administration. Based on the safety, immunogenicity, PK and PD data, the SRC will determine what dose to apply in the next cohort.

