14.1 Drug exposure

Upon provision of signed informed consent, patients are assigned a patient number and allocated to a dose cohort in strict consecutive order. Thus, the first 3 enrolled patients are assigned to Cohort 1 and administrations of SOBI003 at 3 mg/kg/week; for Cohorts 2 and 3, dose levels of 10 mg/kg/week and 20 mg/kg/week are planned.

At the time of the 1st SOBI003 infusion, the patient should not have any clinically significant evidence of an ongoing infection, or an ongoing treatment with antibiotics. In such cases, the 1st infusion should be postponed until the infection has resolved.

SOBI003 is administered as weekly i.v. infusions over a period of time of 4 hours. The study treatment period comprises 24 weekly infusions. For each weekly visit, date and time of administration will be recorded in the eCRF, as well as reasons for infusion stop (if any), dose level, SOBI003 volume, total infusion volume administered, and dosing action taken (e.g., “withdrawn”). All data will be listed.

In addition, actual dose received in mg, actual dose level received in mg/kg (see Section 8.4.8), and study treatment exposure in weeks will be calculated (see Section 8.4.2). These data will be listed and summarized.

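### The dose-proportionality limits in SAP 15.7 are computed from a 20 mg/kg dose level that the planned analysis no longer contains

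*SAP*

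**What the plan says.** SAP 15.7 fits log(PK parameter) = μ + β·log(dose) and compares the 90% confidence interval for β with a critical interval. The definition comes first: "First the ratio (r) of the highest dose level to the lowest dose level will be calculated". The limits are then 1 + log(0.5)/log(r) and 1 + log(2.0)/log(r). Next the SAP inserts a value: "r value is based on the ratio between highest and lower dose levels of SOBI003 and equals to" 20/3 = 6.667. It concludes that the "critical interval to declare dose linearity will be 0.63 to 1.37 for 90% CI of the slope estimate".

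Four other places bear on which dose levels are in the analysis:

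- **SAP 4.1**, on the February 2020 decision to discontinue the programme: "Thus, Cohort 3 in the FIH study (SOBI003-001) will not be started", and "Statistical analysis for the FIH study (SOBI003-001) CSR will be done for Cohort 1 and 2".
- **SAP 14.1**, after giving 3 mg/kg/week for Cohort 1: "for Cohorts 2 and 3, dose levels of 10 mg/kg/week and 20 mg/kg/week are planned". The Protocol synopsis agrees: "The planned mid and maximum dose levels for Cohorts 2 and 3 are 10 mg/kg and 20 mg/kg, respectively".
- **Protocol 7.4.1**, footnote to Table 2, for Cohorts 2 and 3: "Actual dose levels are determined by SRC".
- **SAP 8** confines every analysis in the plan to SOBI003-001 data up to Week 24, although the database also holds extension-study data.

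**The concern.** The SAP defines r by the dose levels under study, then uses a level assigned only to a cohort that will not exist. The same SAP version records the discontinuation, and SAP 17 drops the heparan sulfate mixed models because of it. SAP 17 does not mention the proportionality limits, and Table 14.3.4.9.4 (the power-model analysis) is still in the table index. So this is current text for an analysis that is still planned.

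Extension-study dosing cannot supply the missing level. The Safety Review Committee may set doses for extension patients (SAP 5.1), but SAP 8 keeps those data out.

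At stake is a stated decision threshold. A study report that follows the printed numbers would draw its conclusion against limits the SAP does not define. One that follows the formula would use different limits. If this is left open, the choice could be made after the slope is known.

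**Working it through.** **Inputs.** The formula and r = 20/3 come from SAP 15.7. The planned levels of 3, 10 and 20 mg/kg for Cohorts 1, 2 and 3 come from SAP 14.1 and the Protocol synopsis. The cohorts analysed (1 and 2) come from SAP 4.1.

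**Formula.** Because log(0.5) = −log(2), the limits are 1 ± ln 2 / ln r. The base of the logarithm cancels.

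**Reproducing the SAP figure.** For r = 20/3 = 6.667, ln 2 / ln r = 0.3654 and the limits are 0.635 to 1.365. This matches the printed 0.63 to 1.37. The arithmetic is right; the input is not.

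**With the planned levels of the cohorts analysed.** For r = 10/3 = 3.333, ln 2 / ln r = 0.6931/1.2040 = 0.5757 and the limits are 0.424 to 1.576. The width rises from 0.73 to 1.15.

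**What the printed limits mean over the narrower range.** A slope β implies a dose-normalised ratio of r^(β−1) between the highest and lowest dose. The formula is built so that this ratio runs from 0.5 to 2.0 at the limits. At r = 3.333 the unrounded SAP limits give 3.333^(±0.3654) = 0.644 to 1.553. The rounded limits 0.63 and 1.37 give 0.641 to 1.561.

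**Sensitivity to the Cohort 2 level.** The documents do not report it. Cohort 1 is 3 mg/kg throughout. The 7.5 and 15 mg/kg rows are assumptions used only to show the range.

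| Cohort 2 level (mg/kg) | r | Limits from the SAP formula | Ratio implied by the SAP's 1 ± 0.3654 |
|---|---|---|---|
| 7.5 (assumed) | 2.5 | 0.24 to 1.76 | 0.72 to 1.40 |
| 10 (planned) | 3.333 | 0.42 to 1.58 | 0.64 to 1.55 |
| 15 (assumed) | 5 | 0.57 to 1.43 | 0.56 to 1.80 |
| 20 (planned for Cohort 3 only) | 6.667 | 0.63 to 1.37 | 0.50 to 2.00 |

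Protocol 7.4.5.2 also allows the next cohort to repeat the same level or use a lower one. A repeat of 3 mg/kg gives r = 1, ln r = 0 and no interval. A lower level gives a finite r with 3 mg/kg as the highest dose; r would again be 6.667 at 3/6.667 = 0.45 mg/kg.

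**Illustration of the practical effect.** The inputs here are assumptions, not document figures: three patients per cohort, one value each, no covariate, 4 degrees of freedom, an estimated slope of exactly 1 (the most favourable case), and the whole 90% interval required to lie inside the limits. With s the between-patient SD on the log scale, the half-width at 3 versus 10 mg/kg is 2.132·s·√(2/3)/ln(3.333) = 1.446·s.

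- It equals 0.3654 at s = 0.253. With CV = √(exp(s²) − 1), that is about 26%.
- It equals 0.5757 at s = 0.398, a CV of about 41%.

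Under these assumptions, proportionality could be declared up to a CV of about 26% with the printed limits and about 41% with the formula's limits.

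**The case against.** The strongest case on the other side concerns weight. SAP 15.7 calls the analysis exploratory, and the protocol has no dose-proportionality objective or endpoint. The programme has been discontinued with three patients in each of two cohorts. The slope, its interval, the plots and the correlation analyses do not use r. A programmer who applies the definition to the cohorts analysed would reach the right limits unaided. All of this stands and limits the consequence. It does not settle the text, because the SAP also says flatly what the interval will be, and for the planned cohorts the definition and the number disagree.

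A second objection is that the Cohort 2 dose is set by the Safety Review Committee and is not reported, so 0.42 to 1.58 cannot be called the correct interval outright. That also stands. But the printed limits would be right only at a Cohort 2 level of 20 mg/kg, or at the far lower 0.45 mg/kg, and no passage gives either for Cohort 2.

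A third is that limits that are too narrow err on the safe side. That holds for a Cohort 2 level above 3 and below 20 mg/kg, if declaring proportionality needs the whole interval inside the limits. The SAP's wording, that proportionality is rejected when the interval falls outside, does not establish that reading. Limits that are too narrow also make rejection easier: an interval lying wholly above 1.37 but starting below 1.58 would be rejected under the printed limits and not under the formula's.

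**Conclusion.** The inconsistency is real. SAP 15.7 takes its limits from a dose level that SAP 4.1 and SAP 8, read with the planned cohort doses, leave out of the analysis. At the planned levels of the two cohorts analysed, the SAP's own formula gives 0.42 to 1.58 rather than 0.63 to 1.37. The contradiction itself is certain on the text. The replacement interval assumes that Cohort 2 was assigned 10 mg/kg.

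The effect is confined to the declared conclusion on proportionality in an exploratory analysis; no estimate changes. It should be corrected because it is a stated decision threshold and is easily put right.

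**What to change.** In SAP 15.7, replace the fixed r = 20/3 with the ratio of the highest to the lowest assigned cohort dose level among the cohorts analysed, and recompute the limits from the formula already given. If those levels are 3 and 10 mg/kg, print r = 3.333 and 0.42 to 1.58. If the two cohorts share one level, state that no interval can be formed.

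Specify assigned levels rather than the per-visit dose received (SAP 8.4.8 and 14.1), so that r does not depend on extreme individual infusions. For example, if doses varied by an assumed 5% and r came from the extremes, r = 10.5/2.85 = 3.684 and the limits would move to 0.47 to 1.53.

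A separate small clarification, independent of r, belongs in the same edit: state that proportionality is declared only when the whole 90% interval lies inside the limits, and say how an interval that straddles a limit is reported.

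The correction of r costs one or two sentences before the PK analysis is run and needs no new data.

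### The two Pearson correlations in SAP 15.7 are very unlikely to show dependably whether total dose (mg) or mg/kg dose drives SOBI003 exposure

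*SAP*

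**What the plan says.** After the power model, SAP section 15.7 adds a second analysis. Cmax, Cmin, end-of-infusion concentration, AUC0-168h and AUC0-inf are paired with total dose and with weight-adjusted dose, and these "will be investigated using Pearson correlation analysis to estimate which type of dosing has an effect on pharmacokinetics of SOBI003". Confidence limits come from Fisher's z transformation: "Alpha value and a null hypothesis value will be specified for 95% two-sided CI". The section adds that "CI's in addition to p-value will be calculated to demonstrate the validity of correlation". It gives no rule or test for comparing the two correlations.

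The number of points follows from two other places. SAP section 4.1 records that "3 patients had been included in Cohort 1 and 3 patients in Cohort 2 of the FIH study", and that "Statistical analysis for the FIH study (SOBI003-001) CSR will be done for Cohort 1 and 2". The tables index (SAP 19.2, Table 14.3.4.9.5) lists "Dose Proportionality for SOBI003 PK parameters by Visit using Pearson Correlation Analysis – PK Analysis Set". A correlation by visit has one point per child, so at most six.

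On dose, SAP section 14.1 puts Cohort 1 at 3 mg/kg and says that "for Cohorts 2 and 3, dose levels of 10 mg/kg/week and 20 mg/kg/week are planned". The dose actually given in Cohort 2 is not stated.

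SAP section 17 withdraws the heparan sulfate mixed models because the programme stopped. It does not mention the Pearson analysis.

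**The concern.** The two dosing bases differ only through body weight. Total dose equals mg/kg dose times weight, so a large step in mg/kg between cohorts raises both predictors together and pulls exposure up with both. Two high correlations then show that exposure rises with dose. They say little about whether weight-based dosing evens out exposure between lighter and heavier children.

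Each interval and p-value describes one correlation on its own, and neither isolates weight. A table with two apparently valid correlations invites the reader to take the larger as the answer. Whether mg/kg dosing gives weight-independent exposure is a useful question for this study, and the planned table could answer it wrongly while looking well supported.

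**Working it through.** **The plan's own figure.** The only number computed in section 15.7 belongs to the power model. With r = 20/3 = 6.667, the limits are 1 + ln(0.5)/ln(6.667) = 0.635 and 1 + ln(2)/ln(6.667) = 1.365, which reproduces 0.63 to 1.37. The plan gives no precision or decision figure for the Pearson analysis.

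**Inputs.**
- n = 6, three per cohort (SAP 4.1), one point per child per visit (SAP 19.2).
- 95% two-sided Fisher intervals (SAP 15.7).
- Dose 3 mg/kg in Cohort 1. For Cohort 2, 10 mg/kg is assumed from the plan in SAP 14.1.
- Weights: assumed uniform on 10-20 or 10-25 kg. Eligible age is 12 to 72 months (SAP 4.2.1), and Protocol 7.2 takes 10 kg for an average one-year-old.
- Between-patient CV: not in the documents; 20 to 40% assumed, with wider values as a check.

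**Fisher interval at n = 6.** The half-width on the z scale is 1.96/√(6 − 3) = 1.132. For r = 0.90, z = 1.472, so the interval runs from tanh(0.340) = 0.33 to tanh(2.604) = 0.99. For two intervals not to overlap, the z values must differ by more than 2 × 1.132 = 2.26. Against r = 0.90, the other correlation would have to exceed tanh(1.472 + 2.263) = 0.9989.

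**Simulation.** Exposure = mg dose / CL, with CL = W^b × log-normal error, and 40,000 trials per setting. With b = 1, exposure follows mg/kg dose; with b = 0, it follows total mg. Values of 0.5 and 0.75 were also run.

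CV 20-40%, weights 10-20 or 10-25 kg:
- median correlation between mg and mg/kg dose: about 0.93 to 0.96;
- median r with exposure, over all four values of b: 0.82 to 0.96 for mg/kg and 0.82 to 0.97 for mg;
- the two 95% intervals fail to overlap in at most about 0.5% of trials;
- both intervals lie above zero in 43 to 95% of trials;
- the larger r names the wrong basis in about 17 to 37% of trials when b is exactly 0 or 1;
- at b = 0.5, midway between the bases, mg/kg has the larger r in 48 to 49%.

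Weights 10-25 kg, from a separate run that also covers CV 50%:

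| CV | Truth | Median r, mg/kg | Median r, mg | Intervals overlap |
|---|---|---|---|---|
| 20% | mg/kg | 0.96 | 0.90 | 99.8% |
| 20% | total mg | 0.90 | 0.97 | 99.5% |
| 30% | mg/kg | 0.92 | 0.86 | 99.9% |
| 30% | total mg | 0.86 | 0.93 | 99.9% |
| 50% | mg/kg | 0.81 | 0.77 | above 99.9% |
| 50% | total mg | 0.77 | 0.85 | above 99.9% |

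**Limits of the result.** At low variability the picture changes. Over weight ranges of 12-20, 10-25 and 10-30 kg, the intervals separate in up to 8% of runs at CV 10% and up to 32% at CV 5%.

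**A less conservative comparison.** Overlap of two marginal intervals is a blunt way to compare correlations that share data. Williams' test for dependent correlations detects the difference in 16 to 24% of runs at CV 20% and 12 to 17% at CV 30% (weights 12-20 and 10-25 kg). A proper comparison would therefore also be weak.

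**What isolates weight.** AUC = (mg/kg × W)/W^b, so log AUC = constant + log(mg/kg) + (1 − b) log W. The coefficient of log W, at fixed mg/kg dose, is the quantity asked about: 0 if mg/kg drives exposure, 1 if total mg does.

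**The case against.** Several objections have force.

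- *The analysis is exploratory and one of several.* Section 15.7 calls dose proportionality exploratory. Its power model may take weight as a covariate, section 15.7 also plans scatter plots against both dose measures, section 15.5.3 presents PK by body weight, and section 3.4.3 lists population PK with covariates. The programme has stopped, and neither the primary endpoint nor any stated decision rests on this table. This limits the consequence. But the covariate is optional and not tied to the dosing-basis question, and none of these outputs corrects the reading given to the Pearson table.
- *Interval overlap is not the plan's criterion.* True: section 15.7 states no rule for comparing the correlations. Overlap is used here only to show how little the output discriminates, and the dependent-correlation test leads to the same conclusion.
- *Six children cannot settle the question by any method.* Largely true. A wide interval on the weight slope at least shows this, whereas two high correlations hide it.

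A reader might also infer that the p-values test zero correlation. The documents do not say so: section 15.7 leaves the null value to be specified. The criticism does not depend on it, because no single null value for one correlation compares mg with mg/kg.

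**Conclusion.** The point holds as a limit on what the planned output can show. With six children in two cohorts, the two correlations are very unlikely to distinguish the dosing bases dependably. Both are high under either truth, their intervals overlap in about 99% or more of trials at CV 20-40%, and choosing the larger is wrong in about 17 to 37% of trials when one basis is exactly right.

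Three stronger readings are not supported. The intervals do not always overlap; separation becomes appreciable at a CV of 10% or less. The larger correlation is not a coin toss when one basis is exactly right, since it is then correct in about 63 to 83% of trials. And the correlations are not certain to be high: at CV 50% both exceed 0.7 in only 53 to 68% of runs.

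The figures rest on assumed doses, weights and variability that the documents do not confirm for the treated children. The structural point does not: total dose contains mg/kg dose, and neither correlation isolates weight. The matter is worth correcting because the remedy is cheap, but it does not touch the primary safety analysis.

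**What to change.** For this question, replace the Pearson table with a descriptive regression, per visit, of log(AUC0-168h) on log(mg/kg dose) and log(body weight). This is the existing power model with the weight covariate made mandatory. Report the weight slope with its 90% interval, and say how to read it: 0 means mg/kg dosing gives weight-independent exposure, 1 means total mg drives exposure.

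The simpler regression of log(AUC per mg/kg) on log weight may be shown as a sensitivity analysis. State that it assumes dose proportionality. SAP section 4.1 gives priority to younger patients as cohorts fill, so lighter children may sit in the lower-dose cohort, and a departure from proportionality could then pass for a weight effect. With weights ordered by cohort, a true dose slope of 0.8 or 1.2, CV 20% and weights 10-25 kg, the weight slope shifts by about −0.44 or +0.44, and coverage of the 90% interval falls from 90% to 76%.

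Drop the correlation p-values and the sentence about demonstrating validity. Keep the planned scatter plots. Record the change in SAP section 17.

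The cost is SAP wording and one small program. The downside is imprecision, which should be stated: the median 90% half-width for the weight slope is about 0.84 (CV 20%, 10-25 kg) to 2.2 (CV 40%, 10-20 kg) with log dose in the model, and about 0.69 to 1.8 without it. The distance between the two hypotheses is 1, so the result may well be inconclusive.
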